6.2.3.5.3 CGI-I

Clinical Global Impression - Investigator (CGI-I) includes a single item that asks the investigator to describe the subject's overall severity of uterine fibroids symptoms with the response options "none", "very mild", "mild", "moderate", "severe" and "very severe".

CGII will be summarized by a frequency table with the number of observations and percentage by treatment group and visit. Stacked column bar charts will be created by visit.

6.2.3.6 Variables related to laboratory parameters

6.2.3.6.1 Change from baseline in hemoglobin, hematocrit, and ferritin

Hemoglobin, hematocrit, and ferritin will be analyzed in the same way as laboratory measurements described in section other safety variables (see section 6.5.3.6)

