In general, the last valid, non-missing value prior to the Reference start date will be considered as baseline value. For variables analyzed by 28-day periods, the baseline period corresponds to the last 28 days before the reference start date. This definition does not apply to analyses related to menstrual blood loss where a specific definition for baseline menstrual blood is defined (see baseline menstrual blood loss for 28 days).

Bleeding caused by conducting endometrial biopsy

If an endometrial biopsy was conducted, bleeding on the day of intervention and the 3 days thereafter will not be considered in the bleeding related evaluation, i.e., bleeding/spotting on the day of biopsy and 3 days thereafter will not be considered as day(s) with bleeding/spotting and MP values will be set to 0 mL. This rule is applicable for all bleeding related efficacy analyses.

A biopsy will be regarded as conducted if the intervention was attempted, either successfully or unsuccessfully. Successful means that the date of biopsy is given and 'Biopsy sample obtained - Not done' is not ticked in the eCRF. Unsuccessful means that the date of biopsy is given, 'Biopsy sample obtained - Not done' is ticked in the eCRF, and the reason 'Unsuccessful attempt' is selected.

Baseline menstrual blood loss for 28 days

Baseline menstrual blood loss for 28 days is defined as the sum of volume of menstrual blood loss data of respective days in the baseline cycle. If baseline cycle length is more than 28 days, only data from the first day of cycle to the 28th day of cycle will be used. If baseline cycle length is less or equal than 28 days, data from the first day of cycle to the last day of cycle will be used.

Baseline menstrual cycle

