6.5.3.6 Laboratory parameters

For immunology and coagulation parameters Intervals ‘BL/Post baseline’ will be used, while for all other laboratory measurements the following time intervals will be considered:

- Intervals C (according to Figure 4-1)

The tabulation will follow in principle the Bayer Global Standard Tables catalogue (currently V 4.0 default), with the necessary modifications like for time interval presentation instead of visit presentation.

The maximum or minimum measurement within the time interval will be used for calculations, following a worst-case approach (for details please refer to Appendix 2). Scheduled as well as unscheduled measurements will be considered.

Central as well as local lab measurements are available. Summary statistics will be provided based on central lab. Local lab measurements will be listed.

Values below the lower limit of quantification (LLOQ) will be set to LLOQ/2.

Values above the upper limit of quantification (ULOQ) will be set to ULOQ.

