Appendix 2 : The maximum or minimum measurement for laboratory parameters

Table 9-3 The maximum or minimum measurement for laboratory parameters

Laboratory category	Laboratory test	lowest	highest
VITAMINS	25-Hydroxyvitamin D	X	
COAGULATION	Activated Partial Thromboplastin Time		X
HORMONES	Adrenocorticotrophic Hormone	X	X
GENERAL CHEMISTRY	Alanine Aminotransferase		X
GENERAL CHEMISTRY	Albumin	X	
GENERAL CHEMISTRY	Alkaline Phosphatase		X
IMMUNOLOGY	Alpha-1 Antitrypsin		X
IMMUNOLOGY	Anti Mitochondrial Antibody		X
IMMUNOLOGY	Antinuclear Antibodies		X
GENERAL CHEMISTRY	Aspartate Aminotransferase		X
HEMATOLOGY	Basophils	X	X
HEMATOLOGY	Basophils/Leukocytes		X
GENERAL CHEMISTRY	Bilirubin		X
URINALYSIS	Bilirubin		X
URINALYSIS	Blood		X
GENERAL CHEMISTRY	Bone Specific Alkaline Phosphatase		X
MICROBIOLOGY	Brucellae		X
GENERAL CHEMISTRY	Calcium	X	X
PROTEINS	Ceruloplasmin		X
GENERAL CHEMISTRY	Chloride		X
GENERAL CHEMISTRY	Cholesterol		X
	Choriogonadotropin Beta		X
HORMONES	Choriogonadotropin Beta		X

URINALYSIS	Choriogonadotropin Beta		X
HORMONES	Cortisol	X	X
GENERAL CHEMISTRY	Creatine Kinase		X
GENERAL CHEMISTRY	Creatinine		X
IMMUNOLOGY	Cytomegalovirus DNA		X
GENERAL CHEMISTRY	Direct Bilirubin		X
HEMATOLOGY	Eosinophils		X
HEMATOLOGY	Eosinophils/Leukocytes		X
IMMUNOLOGY	Epstein-Barr Capsid IgG Antibody		X
IMMUNOLOGY	Epstein-Barr Capsid IgM Antibody		X
IMMUNOLOGY	Epstein-Barr Nuclear Antigen 1 IgG Ab		X
HEMATOLOGY	Ery. Mean Corpuscular Hemoglobin		X
HEMATOLOGY	Ery. Mean Corpuscular Volume	X	
HEMATOLOGY	Erythrocytes	X	
HORMONES	Estradiol	X	
GENERAL CHEMISTRY	Ferritin	X	
HORMONES	Follicle Stimulating Hormone		X
GENERAL CHEMISTRY	Gamma Glutamyl Transferase		X
URINALYSIS	Glucose		X
IMMUNOLOGY	HCV PCR Viral Load		X
GENERAL CHEMISTRY	HDL Cholesterol	X	X
HEMATOLOGY	Hematocrit		X
HEMATOLOGY	Hemoglobin	X	
GENERAL CHEMISTRY	Hemoglobin A1C		X
IMMUNOLOGY	Hepatitis A Virus Antibody		X
IMMUNOLOGY	Hepatitis A Virus Antibody IgM		X
IMMUNOLOGY	Hepatitis B Virus Core Antibody		X
IMMUNOLOGY	Hepatitis B Virus DNA		X
IMMUNOLOGY	Hepatitis B Virus Surface Antibody		X
IMMUNOLOGY	Hepatitis B Virus Surface Antigen		X
IMMUNOLOGY	Hepatitis C Virus Antibody Surface		X
IMMUNOLOGY	Hepatitis D Virus Antibody		X
IMMUNOLOGY	Hepatitis D Virus IgG Antibody		X
IMMUNOLOGY	Hepatitis D Virus IgM Antibody		X
IMMUNOLOGY	Hepatitis D Virus RNA		X
IMMUNOLOGY	Hepatitis E Virus Antibody		X
IMMUNOLOGY	Hepatitis E Virus IgG Antibody		X
IMMUNOLOGY	Hepatitis E Virus IgM Antibody		X
IMMUNOLOGY	Hepatitis E Virus RNA		X

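### Efficacy change in hemoglobin and ferritin takes the lowest value per interval and hematocrit the highest, each against a single last baseline value, so intervals with more than one draw give biased changes in opposite directions

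*SAP*

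**What the plan says.** Section 6.2.3.6.1 gives no value-selection rule of its own for the change from baseline in the three red-cell and iron variables. It refers to the safety laboratory section: "Hemoglobin, hematocrit, and ferritin will be analyzed in the same way as laboratory measurements described in section other safety variables".

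Section 6.5.3.6 presents these parameters by Intervals C (treatment periods, breaks and follow-up intervals) and states: "The maximum or minimum measurement within the time interval will be used for calculations, following a worst-case approach". It adds: "Scheduled as well as unscheduled measurements will be considered". Summary statistics use central laboratory values.

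Table 9-3 in Appendix 2 sets the direction. For "HEMATOLOGY Hemoglobin X" and "GENERAL CHEMISTRY Ferritin X" the mark stands in the lowest column. For "HEMATOLOGY Hematocrit X" it stands in the highest column.

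For baseline, Section 4.5 says that "the last valid, non-missing value prior to the Reference start date will be considered as baseline value". No worst-case selection is stated for it.

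Sections 6.2.3.6.2 (hemoglobin above 12 g/dL and hematocrit above 36%) and 6.2.3.6.3 (hemoglobin at or below 10.9 g/dL) also tabulate by Intervals C. They neither name the value to be classified nor refer to Section 6.5.3.6.

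**The concern.** A worst-case value suits a safety table, where the question is whether a subject ever reached a worrying level. A change-from-baseline efficacy summary asks where the subject ended up. Here each post-baseline interval contributes the extreme of however many draws it holds, and baseline contributes one value. That asymmetry moves the mean change even when nothing has changed, and by more when there are more draws. While hemoglobin is rising, the lowest value in a TP is usually the earliest, so the level reached by the end of the TP is left out.

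Hematocrit goes the other way. Two closely linked measures, named in one sentence, would be summarised from opposite extremes. Because unscheduled draws count, the result also depends on how often each subject was sampled. Section 4.4 makes this efficacy analysis final, so these tables will be the record.

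**Working it through.** **Inputs.** From the SAP: the selection rule, the directions, the single baseline value, and a nominal TP of 3 x 28 = 84 days (Section 4.5; group B also uses 84-day intervals). The SAP gives no draw days, expected hemoglobin change or within-subject SD, so there is no planned figure to reproduce and the following are assumptions: a gain of 1 or 2 g/dL by day 84; a linear path or an early-rising one (28-day time constant); within-subject SD 0.3 or 0.5 g/dL; one to four draws per TP.

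**Step 1: no true change.** The expected minimum of 2, 3 or 4 independent normal values lies about 0.56, 0.85 or 1.03 SD below the mean. The lowest value minus one baseline value therefore averages:
- two draws: 0.56 x 0.3 = 0.17 to 0.56 x 0.5 = 0.28 g/dL too low;
- three draws: 0.85 x 0.3 = 0.25 to 0.85 x 0.5 = 0.42 too low;
- four draws: 1.03 x 0.3 = 0.31 to 1.03 x 0.5 = 0.52 too low.

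By symmetry, a highest-value rule is too high by the same multiples of the SD.

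**Step 2: one noise-free illustration.** Assume a baseline of 10.5 g/dL, a linear rise to 12.3 by day 84, and draws on days 28 and 84. The day-28 value is 10.5 + 1.8 x 28/84 = 11.1. The rule reports 11.1 - 10.5 = +0.6; the last value gives +1.8.

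**Step 3: first TP by simulation** (200,000 subjects per scenario). Share not shown = 1 - (mean change using the minimum) / (mean change using the last value). The last value recovers the assumed gain in every scenario.

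| Draws in TP1 (assumed days) | Within arm, linear | Within arm, early-rising | Difference from flat group B, linear |
|---|---|---|---|
| 1 (84) | 0% | 0% | 0% |
| 2 (42, 84) | 50-60% | 21-38% | 32-42% |
| 3 (28, 56, 84) | 67-85% | 35-59% | 43-54% |
| 4 (1, 28, 56, 84) | 100-118% | 96-107% | 67-84% |

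The last row matters because baseline must precede the reference start date and the treatment phase begins on it. A draw dated on the start day therefore falls in TP1.

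**Step 4: later TPs.** Once hemoglobin has levelled off, only the noise part remains: 0% of the gain with one draw, 8-28% with two, 13-42% with three and 15-52% with four.

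**Step 5: the highest-value rule.** In the same set-up, the maximum exceeds the assumed gain by up to 20% with two draws (1.20 against 1.00) and up to 31% with three (1.31 against 1.00). This carries over to hematocrit only if its ratio of gain to SD is similar. It is a within-group statement. For a linear gain of 1.00 with SD 0.5 and three draws, the treated mean is 1.18 and a flat group B shows +0.42, a difference of 0.76. The minimum rule gives 0.57 in that scenario.

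**Step 6: threshold tables.** If the Section 6.5.3.6 rule is carried into Section 6.2.3.6.2, the lowest hemoglobin is set beside the highest hematocrit, possibly from different draws. The woman in Step 2 would be classified at 11.1, not above 12, although she ended at 12.3. If the rule is not carried over, the value is undefined.

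**The case against.** The best defence is that the plan is deliberately conservative. Its efficacy section uses worst values elsewhere: the UFS-QoL takes the worst measurement in the interval (Section 6.2.3.5.2), and ultrasound takes the smallest baseline volume and the largest later one (Section 6.2.3.3). For hemoglobin the rule works against the study drug. This does not carry through, because the highest hematocrit favours improvement within a group, so the directions follow no single conservative policy. Where the plan wanted an efficacy worst case for ultrasound, it wrote explicit rules for baseline and later intervals; Section 6.2.3.6.1 has none.

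Other objections stand and limit the point. The size cannot be derived from the SAP, because the number and timing of draws are not given. The masking is within an interval and mainly in TP1; a sustained gain still shows in later TPs, whose minimum comes from later draws. The same rule applies to group B, so part of the noise bias cancels between groups. Intervals C also include breaks of variable length, so they are not all 84-day periods. There is no primary efficacy variable (Section 6.2.1), the secondary one is number of bleeding days (Section 6.2.2), and these laboratory variables carry no test.

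A reader might infer that the plan largely hides recovery from anemia, or that the threshold tables will misclassify recovered women. The SAP supports neither as fact. With one draw per TP nothing is lost, and the threshold sections do not say that they use the worst-case value.

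**Conclusion.** The point holds in limited form. By its stated rule, the plan compares an extreme value per interval with a single baseline value, so with two or more draws hemoglobin and ferritin recovery is understated and the within-group hematocrit gain overstated. For hemoglobin in the first TP, the share not shown is 0% with one draw, about 21-60% with two and 35-85% with three. The difference from a flat group B loses about 32-42% with two draws and 43-54% with three under a linear gain. A start-day draw counted in TP1 could remove essentially all of the first-TP within-arm gain.

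These figures rest on the assumed gains, paths, SDs and draw days; no ferritin values were simulated. The direction of the bias rests on the SAP alone, including the position of the hematocrit mark in Table 9-3. Separately, Sections 6.2.3.6.2 and 6.2.3.6.3 leave the classified value unspecified. The point is worth correcting because the tables are final, but it touches descriptive variables only.

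**What to change.** In Sections 6.2.3.6.1 to 6.2.3.6.3, state that the last central laboratory value in each Interval C is used for hemoglobin, hematocrit and ferritin, as applicable. Write this into each section and do not rely on the reference to Section 6.5.3.6. Limit the worst-case selection of Section 6.5.3.6 and Appendix 2 to the safety laboratory tables.

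The cost is a change of SAP wording and one additional value-selection flag in the analysis dataset. Efficacy and safety tables will then show different values for the same parameter and interval, which a footnote should explain.

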6.2.3.6.2 Percentage of subjects with normal hemoglobin >12 g/dL and normal hematocrit >36%

Frequency tables with number of observations and percentage will be displayed by treatment period within treatment group and by Intervals C. A listing will be provided.

6.2.3.6.3 Percentage of subjects with hemoglobin ≤ 10.9 g/dL)

Frequency tables with number of observations and percentage will be displayed by treatment period within treatment group and by Intervals C. A listing will be provided.

6.3 Pharmacokinetics/pharmacodynamics

A separate Pharmacokinetic (PK)/Pharmacodynamic (PD) Evaluation Plan, providing details of the model development and evaluation will be provided before the beginning of the population PK analysis. Evaluation of the data will be presented in a separate PK/PD Evaluation Report.

6.4 Exploratory biomarker analysis

Evaluation of biomarker related analysis will be performed and detailed in a separate document.

6.5 Safety

The safety analysis will be performed on the observed safety data for the safety analysis population.

6.5.1 Primary safety variable

The primary safety variable is the percentage change in BMD of lumbar spine (using the central reading results) from baseline to about one year after SoT. One year is defined as ‘Month 12 on treatment’ in Table 6-1, i.e. Day 300 after reference start date to Day 420 after reference start date, but no later than the reference end date + 60 days.

The primary safety variable will be analyzed using descriptive statistical methods and two-sided 95% confidence interval (CI) for the mean difference for the percentage change in BMD of lumbar spine from baseline to about one year after SoT will be calculated for each vilaprisan treatment group as compared to treatment group B. Additionally, two-sided 95% CI for each treatment group will be calculated. The primary variable is assumed to be at least approximately normally distributed.

For the percentage change in BMD of lumbar spine from baseline to other time points defined in Table 6-1, the descriptive statistics will also be provided by treatment group.

The percentage change in BMD of lumbar spine from EoT BMD will also be evaluated using summary statistics by treatment group and time interval or month for post treatment period defined in Table 6-1.

The time intervals and month named in Table 6-1 will be presented in tables and figures unless otherwise specified. Month equals 30 days.

Table 6-1: Definition of month and time intervals for BMD summary

	Month	Time interval
Baseline	Baseline	Baseline if no Visit 2-repeat scan exists, Visit 2 scan will be used as baseline. Otherwise, Visit 2 -repeat scan will be used. The BMD baseline visit will be marked in the dataset transferred from ICON’s Medical Imaging group. (refer to section 4.5)
On treatment period : From reference start date to reference end date + 60 days	Month 1	N/A
	Month 2	If a BMD value performed after the reference start date has been marked as baseline value, it will be analyzed as baseline value and will be excluded from the analysis for on treatment period.
	Month 3	
	Month 4	
	Month 5	Month 6 on treatment Day 120 after reference start date to Day 240 after the reference start date, but no later than the reference end date + 60 days
	Month 6	
	Month 7	
	Month 8	
	Month 9	N/A
	Month 10	Month 12 on treatment Day 300 after reference start date to Day 420 after reference start date, but no later than the reference end date + 60 days
	Month 11	
	Month 12	
	Month 13	
	Month 14	
	>Month 14	N/A In case of more than one measurement > Month 14, the worst measurement within the time interval will be used for calculations.

	N/A	EoT BMD Reference end date ± 60 days If two measurements are available during the EoT BMD time interval, the measurement closest to the reference end date will be use as EoT BMD measurement.
Post treatment period: After reference end date + 60 days	Month 3	N/A
	Month 4	Month 6 post treatment
	Month 5	Day 120 after the reference end date to Day 240 after the reference end date
	Month 6	
	Month 7	
	Month 8	
	Month 9	N/A
	Month 10	Month 12 post treatment
	Month 11	Day 300 after the reference end date to Day 420 after the reference end date
	Month 12	
	Month 13	
	Month 14	
	>Month 14	N/A In case of more than one measurement > Month 14, the worst measurement within the time interval will be used for calculations.
	N/A	EoFUP BMD The last measurement, but no earlier than the reference end date + 60 days

BMD = bone mineral density; EoT=end of treatment; EoFUP= end of follow-up; N/A=not applicable

Percentage change in BMD of lumbar spine from baseline with frequencies and percentages for the following categories: <-6%, ≥-6% - <-3% , ≥-3% - <-1.5% , ≥-1.5% - ≤0%, >0% - ≤1.5%, >1.5% - ≤3% , >3% - ≤6% and >6% will also be summarized by treatment group. The worst outcome per subject during treatment period will be used in the analyses.

Frequency table for the status of BMD of lumbar spine at EoFUP compared with EoT will be provided by treatment group. The categories for the status of BMD of lumbar spine at EoFUP is defined in Table 6-2. Percentage of recovery is defined as change in BMD of lumbar spine from EoT BMD to EoFUP BMD divided by change in BMD of lumbar spine from Baseline to EoT BMD. It will be evaluated in subjects with partially recovered. Number and percentage of subjects for percentage of recovery by categories of ≥ 75 - < 100%, ≥ 50 - <75%, ≥ 25 - <50% and ≥ 0 - <25% will be provided for subjects with partially recovered.

Table 6-2: Status of BMD of lumbar spine at EoFUP

% change in BMD of lumbar spine from baseline to EoT BMD (x)	% change in BMD of lumbar spine from baseline to EoFUP (y)	Status at EoFUP	Percentage of recovery
< 0	≥ 0	Recovered, completely	≥ 100%

< 0	$x \leq y < 0$	Recovered, partially	$\geq 0\% - <100\%$
< 0	$y < x$	Not recovered or further decrease	Not applicable
≥ 0	≥ 0	No decrease during both treatment and FUP period	Not applicable
≥ 0	< 0	No decrease during treatment period but worsening during FUP period	Not applicable

Mean-deviation plot for the percentage change in BMD of lumbar spine from baseline will be presented by treatment group for the entire study period (treatment period + post treatment period).

Following listings will be provided separately:

- 1) subjects that had at least one DEXA scan during the treatment period with either BMD loss $\geq 6\%$ from baseline to EoT for any location or Z-score ≤ -2 SD for any location.
- 2) subjects with BMD loss $\geq 3\%$ from baseline for any location or Z-score ≤ -2 SD for any location at EoFUP DEXA scan.

During the study, if the baseline scan at Visit 2 was missing or not evaluable based on the evaluation from the Medical Imaging group of ICON, the subject was requested to have a repeat scan. If it's not possible to have this repeat scan performed before the reference start date, this repeat scan was allowed to be performed shortly after the start of the treatment. Considering the BMD will not change quickly, this can be accepted from a medical point of view. If a BMD value performed after the reference start date has been marked as baseline value, it will be analyzed as baseline value and will be excluded from the analysis for on treatment period defined in Table 6-1.

To make a further investigation, an additional analysis for the primary safety variable with subjects excluded who had their baseline scan later than 1 month after start of treatment will be provided.

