- Amendment 10 forming integrated protocol Version 7.0, dated 21 NOV 2019
- Amendment 11 forming integrated protocol Version 8.0, dated 17 FEB 2020
- Amendment 12 dated 06 OCT 2020 (local amendment, valid for Turkey only)

2. Study Objectives

The primary objective of this study is to evaluate the safety of vilaprisan in subjects with uterine fibroids in comparison to nonhormonal medical treatment in accordance with local standard of care.

The secondary objective of this study is to evaluate the efficacy of vilaprisan in subjects with uterine fibroids in comparison to nonhormonal medical treatment in accordance with local standard of care. With the implementation of Protocol Amendment 10 (version 7.0), additional focus will be put on safety evaluations of the endometrium, adrenal glands and skin.

Other objectives of this study are to evaluate the variability in exposure in relation to the efficacy and safety for vilaprisan and to collect patient-reported outcome (PRO) and clinician-reported outcome (ClinRO) data.

3. Study Design

This is an open-label, parallel-group, randomized, multi-center study.

The study was planned to be conducted in Europe, North America, South America, South Africa, and Asia Pacific.

Originally it was planned to randomize 1050 subjects into the study. However, recruitment into the study and treatment in the study were stopped earlier than planned.

An overview of the originally planned study design (before the modifications in study design introduced with Amendment 9, version 6.0 and subsequent amendments) is shown in [Figure 3-1](#).

Eligible subjects were randomized to one of three vilaprisan treatment groups (Groups A1, A2, or A3) or to the standard of care group (Group B).

The planned treatment duration was about one year (Subgroup 1) or two years (Subgroup 2), respectively. The assignment to the 2 subgroups was done in a sequential manner.

After the end of treatment (EoT), subjects were planned to be followed up for 24 weeks (Subgroup 1) or for 12 weeks (Subgroup 2).

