B	SCR up to 90 days	RND	Symptomatic nonhormonal medical treatment as determined by the investigators and/or watch and wait														12 wk FUP	

Groups A1, A2, and A3 treated daily with vilaprisan 2 mg during treatment periods
 Group A1: 4/8 treatment periods of 12 weeks, each separated by 1 bleeding episode (3/1 regimen)
 Group A2: 2/4 treatment periods of 24 weeks, separated by 2 bleeding episodes (6/2 regimen)
 Group A3: 3/6 treatment periods of 12 weeks, each separated by 2 bleeding episodes (3/2 regimen)
 Group B treated with standard of care (SoC) symptomatic nonhormonal medical treatment as determined by the investigators and/or watch and wait.
 B = bleeding episode; FUP = follow-up; RND = randomization; SCR = screening; trt = treatment; wk = week.

The **primary safety variable** is the percentage change in bone mineral density (BMD) of lumbar spine from baseline to about one year after start of treatment (SoT) (please refer to section 6.5.1 for details). With the implementation of Protocol Amendment 10 (version 7.0), the study is being prepared for closure. A thorough safety monitoring is performed in subjects before this closure, including a recovery BMD scan. All subjects who received vilaprisan treatment will be asked to undergo a BMD scan at least 6 months after the last intake of vilaprisan, to document absence of

bone loss or adequate recovery after the end of treatment. Subjects randomized to treatment group B who are still in the study with implementation of Protocol Amendment 10 (version 7.0) should also undergo a BMD scan at the safety closeout visit, unless they had a BMD scan performed within the last 3 months prior to the safety closeout visit.

4. General Statistical Considerations

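### BMD recovery status at end of follow-up is assigned from any last scan from day 60 off treatment, with no breakdown by time, although section 3 places the vilaprisan recovery scan at 6 months or later

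*SAP*

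**What the plan says.** Section 3 describes the closeout scan: "All subjects who received vilaprisan treatment will be asked to undergo a BMD scan at least 6 months after the last intake of vilaprisan". Its purpose is to show absence of "bone loss or adequate recovery after the end of treatment". Group B has no such minimum. Only its subjects still in the study under Amendment 10 are to be scanned at closeout, and a scan in the preceding 3 months excuses them.

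Section 6.5.1, Table 6-1, sets the analysis windows:
- End-of-treatment (EoT) BMD: "Reference end date ± 60 days".
- End-of-follow-up (EoFUP) BMD: "The last measurement, but no earlier than the reference end date + 60 days".
- Post-treatment Month 6: Day 120 to Day 240. Month 12: Day 300 to Day 420.

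The same section states: "Frequency table for the status of BMD of lumbar spine at EoFUP compared with EoT will be provided by treatment group". Table 6-2 defines the status from x (percentage change, baseline to EoT) and y (percentage change, baseline to EoFUP). With x below 0, the subject is completely recovered if y is at least 0, partially recovered if y lies from x to below 0, and not recovered if y is below x. Partially recovered subjects are then sorted into percentage-of-recovery bins. Neither display depends on when the EoFUP scan was taken.

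**The concern.** The status table is the one display that labels individual subjects as recovered or not. Section 3 gives a time after which recovery is to be documented, and the analysis rule does not carry that time over. A scan at about 2 months and one at a year or more receive the same label.

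The shares in each category then depend partly on who returned for a late scan. The SAP expects that not everyone will. Section 3 says subjects are asked, section 4.5 speaks of those who perform the closeout visit, and section 6.1.1 counts those with a closeout BMD. Section 4.4 also analyses the follow-up data available at the 10 February 2021 cut and the rest later, so a subject could be classified on an early scan first and reclassified afterwards.

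The table is shown by treatment group. Because the 6-month request covers vilaprisan only, the time to the EoFUP scan may differ between the columns being compared.

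**Working it through.** The SAP gives no figure to reproduce. The check compares the windows in days and then illustrates the effect on Table 6-2.

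**1. Windows.** Section 6.5.1: "Month equals 30 days".
- Recovery scan in section 3: 6 × 30 = 180 days.
- Earliest accepted EoFUP scan: 60 days.
- Difference: 180 − 60 = 120 days.
- Originally planned follow-up (section 3): 12 × 7 = 84 days in Subgroup 2 and 24 × 7 = 168 days in Subgroup 1. A scan at either point would qualify as EoFUP. Day 84 lies before the Month 6 post-treatment window; day 168 lies inside it.

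**2. Who is affected.** EoFUP takes the last scan, so a subject with a scan at 6 months or later is classified on that scan. An early partial or failed label requires x below 0, y below 0 and no later scan. An early scan with y of at least 0 is called complete recovery. Subjects with x of at least 0 cannot enter either category.

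**3. Illustration without measurement error.** Assume linear recovery, complete at day 180; this is not in the SAP. Recovered share = t/180: day 61 gives 61/180 = 34%, day 84 gives 84/180 = 47%, day 168 gives 168/180 = 93%. A subject on course to recover fully would fall in the 25 to under 50% bin at day 61 or 84.

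**4. Illustration with measurement error.** Assumptions, none from the SAP: true EoT loss of 1% or 2%; linear recovery complete at 180 or 365 days; measurement SD per time point of 0.5% or 1.0%. This gives eight scenarios. The ranges below are among subjects with observed x below 0.

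| Scan day | Complete | Partial | Not recovered |
|---|---|---|---|
| 60 | 1–24% | 43–80% | 17–38% |
| 84 | 1–27% | 43–84% | 9–35% |
| 180 | 7–50% | 42–85% | 0–28% |

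Within each scenario, moving the scan from day 60 to day 180 raises complete recovery by about 6 points (1% to 7%) to 47 points (3% to 50%). It lowers the not-recovered share by about 9 points (37% to 28%) to 24 points (32% to 8%). Early timing shifts the distribution but does not fix any one subject's category.

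**5. Day 60.** The EoT window includes day +60, and so does the EoFUP bound. If a scan on that day is the subject's only one in the EoT window and also her last, then y = x. With x below 0, Table 6-2 labels her partially recovered, at 0%, from a single measurement. The header of the post-treatment period begins after day 60, so the EoFUP row disagrees with its own header.

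**The case against.** The strongest reply is that no analysis rule is broken. Section 3 is a request for data collection in vilaprisan subjects, whereas EoFUP means the end of follow-up and is defined separately. Anyone who returned for the requested scan is classified on it. Timing is also visible elsewhere: section 6.5.1 summarises change from EoT BMD by post-treatment month and window, and plots the whole study period. The table is descriptive, and early scans would tend to understate recovery.

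Much of this stands. A reader might infer that every early scan will be reported as failed or partial recovery. The documents do not support that, for the reasons in step 2 of the working. A reader might also infer that subjects without a closeout scan have at most 84 or 168 days of follow-up. Those are planned durations from a design that section 3 says no longer applies, and the SAP does not place a DEXA scan at those visits.

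A strict 180-day cut is tempting too. It would conflict with the SAP's own Month 6 window and could thin group B, which has no 6-month minimum. Applied to the listing of subjects with loss of at least 3% or a low Z-score at EoFUP, it would remove subjects from a safety display.

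The reply does not remove the core point. The time-based summaries report changes, not recovery status, and nothing in the SAP shows how much of Table 6-2 rests on early scans. On day 60, the period header points to the intended reading, but the row still says otherwise.

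**Conclusion.** The point holds in a limited form. Recovery status and the recovery bins pool scans from day 60 onward with no breakdown, while section 3 ties documented recovery in vilaprisan subjects to about day 180, a gap of 120 days. Subjects with loss at EoT and only an early scan can be counted as partially or not recovered too soon, and scan timing may differ between vilaprisan and group B.

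The number affected is not stated and could be small. The direction, towards understated recovery, assumes that bone density returns gradually. That fits the SAP's own remark, made to justify late baseline scans, that BMD does not change fast. The percentages in steps 3 and 4 of the working are illustrations only. The day-60 overlap is a one-day wording error. The primary one-year comparison is not touched.

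**What to change.** - Reconcile section 3 with Table 6-1 by presenting Table 6-2 and the percentage-of-recovery bins by days from reference end date to the EoFUP scan: before the Month 6 post-treatment window (before Day 120), within it (Day 120–240), and later (after Day 240).
- Base the recovery statement for vilaprisan on scans at about 6 months or later, meaning the Month 6 window onward. Show subjects with only an earlier scan in a separate row. Because the window opens at Day 120, report the distribution of days off treatment alongside.
- Show the same breakdown for group B, so that differences in timing are visible.
- Keep the EoFUP listing of subjects with loss of at least 3% or a low Z-score for all subjects, and add days since reference end date.
- Reword the EoFUP bound so that it starts after reference end date + 60 days, matching the period header.

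The cost is a SAP wording change, one extra breakdown and smaller cells. No new data are needed, and no subject is dropped.
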